2.2. Treatment arms

For the 26-week double-blind period, treatment arms will be defined as:

- S95008 arm.
- Placebo arm.

For the open-label period, treatment group will be defined as:

- Placebo/ S95008 arm: patients assigned to placebo group at W000 and treated by bumetanide 0.5 mg BID in the open-label period.

For the combined period (double-blind+open label periods), treatment group will be defined as:

- S95008 / S95008 arm: patients assigned to bumetanide 0.5 mg BID group at W000 and treated by bumetanide 0.5 mg BID in the open-label period.

It will correspond to allocated treatment by IRS except for safety analyses for which treatment received at W000 will be considered.

3. STATISTICAL METHODS

3.1. General considerations

3.1.1. Descriptive statistics

For **qualitative data**, number of observed values, number and percentage of patients per class will be presented. Unless otherwise specified in the TLG, no class "Missing" is considered.

For **quantitative data**, number of observed values, mean, standard deviation, median, first and third quartiles, minimum and maximum will be presented.

For **events**: number of patients having experienced the event (n), number of events that occurred and number of patients at risk for the event (N) will be presented as well as the patients-years at risk for the event (NPY), the crude incidence rate and the annual incidence rate calculated as follows:

- $NPY = \text{sum of patient's period duration in years.}$
- Crude incidence rate (*i.e.* percentage): $\% = 100 \times (n / N).$
- Annual incidence rate (*i.e.* exposure-adjusted incidence rate): $npv = 100 \times (n / NPY).$ Of note that the annual incidence rate is interpreted as the number of patients with events per 100 patients-years.

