Investigators should always encourage patients to eat foods containing potassium as soon as they know that they will be included in the study. See [Table \(8.2\) 1](#)

Table (8.2) 1 - Foods that have a higher potassium contents

Fruit and nuts	Fruit in particular - bananas, apricots, avocados, blackcurrants, rhubarb, fresh fruit juices Dried fruits eg currants, raisins, prunes, figs, sultanas, are rich sources of potassium All varieties of nut eg almonds, peanuts and walnuts
Potatoes	Potatoes are very rich sources of potassium if they are not boiled Jacket potatoes Ordinary fried chips Instant potato products eg waffles, potato croquettes Potato crisps
Vegetables and pulses	In particular - sprouts, mushrooms, parsnips, spinach, baked beans, kidney beans, lentils
Cereals	Cereals which are high in bran eg bran flakes, all bran, muesli
Biscuits, cakes and sweets	Fruit cakes, fig rolls, muesli bars Chocolate, fudge, liquorice
Milk and dairy products	Drinking milk or eating yoghurts

The first electrolytes monitoring under treatment, in both double and open label periods, should be performed locally no later than 72h after W000 and W026 respectively.

In case of any abnormality, electrolytes will be monitored until return to normal values.

In case of **Mild Hypokalaemia ($3\text{mEq/L} \leq \text{K}^+ < 3.5 \text{mEq/L}$)** arising under study treatment:

→ Foods containing Potassium will be recommended such as leafy green vegetables, tomatoes, citrus fruits, oranges or bananas. An adequate care should be implemented for the hypokalaemia follow up.

→ Patient will be supplied with oral potassium according to investigator's opinion which can be based on local guidelines or local medical practice. The dose could be adapted to hypokalaemia severity or patients' weight.

The following Potassium Chloride doses are recorded only for indicative purposes:

- <20 kg = 400 mg/day (200 bid)
- 20-40 kg = 600 mg/day (300 bid)
- 40 kg = 1200 mg/day (600 bid)

In case of **Moderate Hypokalaemia ($2.2\text{mEq/L} \leq \text{K}^+ < 3 \text{mEq/L}$)** arising under study treatment:

→ The study treatment should be immediately discontinued.

→ An adequate care should be implemented for the hypokalemia follow up.

→ Cardiac monitoring will be performed and level of potassium should be monitored until return within normal range

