8.6. Definition of Adverse event of special interest

An adverse event of special interest (AEOSI) is one of scientific and medical interest or concern regarding the IMP for which recording rules, special documentation such as hospital records and/or adjudication committee could be appropriate. It may be a serious or non-serious AE that may require further investigation in order to characterize and understand.

In the framework of this study protocol AEOSI include any biological Potassium electrolyte abnormality < 3.5 mEq/L.

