3.6. Safety analysis

All safety analyses will be performed on the taken treatment at W000 as following:

- For the double-blind period in the SS by treatment group (S95008 vs placebo).
- For the open-label period: in the SSO on the Placebo/S95008 arm.
- For the combined period: in the SSC on the S95008/S95008 arm.

Six periods are of interest to present accurately the safety endpoints. The start and end date of these periods are summarized in the following table:

Table (3.6) 1 - Definition of periods of emergence for safety events

| Period ID | ANALYSIS PERIOD | START | END |
|------------------|--|--|--|
| #1 | Emergent during the double-blind period | First intake in double-blind | End of double-blind period (including W26) |
| #2 | Treatment Emergent during the double-blind period | First intake in double-blind | Min(Last intake in double-blind + 2 days, First intake in open-label) |
| #3 | Emergent during the open-label period | First intake in open-label (W26 not included) | End of open-label period (including W52 and follow-up) |
| #4 | Treatment Emergent during the open-label period | First intake in open-label (W26 not included) | Last intake in open-label + 2 days (included) |
| #5 | Emergent from the combined period | First intake in double-blind | End of open-label period (including W52 and follow-up) |
| #6 | Treatment Emergent from the combined period | First intake in double-blind | Last intake in open-label + 2 days (included) |

Listing of main safety data (including adverse events) and start/end date of each period will be provided for:

- Patients who had a delay superior to 30 days between the double-blind and the open-label period will be listed separately.

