3.6.1. Adverse events

Definition:

- **Emergent Adverse Events (EAE)** during the double-blind (*resp. open-label, combined*) period are defined as all adverse events which occur in the period #1 (*resp. #3, #5*) (as per table above), or which started strictly before period #1 (*resp. #3, #5*) but which worsen (in terms of intensity) or become serious according to the investigator opinion during period #1 (*resp. #3, #5*).
- **Treatment Emergent Adverse Events (TEAE)** during the double-blind (*resp. open-label, combined*) period are defined as all adverse events which occur in the period #2 (*resp. #4, #6*) (as per table above), or which started strictly before period #2 (*resp. #4, #6*) but which worsen (in terms of intensity) or become serious according to the investigator opinion during period #2 (*resp. #4, #6*).
- **AE starting during the run-in period** are defined as all adverse events which started strictly before period #1.

Analyses:

Number of events as well as number, percentage and annual incidence rate of patients reporting at least one event, presented by primary System Organ Class (SOC), and Preferred Term (PT), will be provided for:

- Serious EAE and deaths for period #1, #3 and #5.
- TEAE, TEAE leading to IMP withdrawal, TEAE requiring new treatment or increase of ongoing treatment, TEAE requiring surgical or medical procedure, TEAE related to IMP, serious TEAE, severe TEAE, non-serious TEAE for periods #2, #4 and #6.

TEAE will be described according to the seriousness, the intensity, the relationship with the IMP, the action taken regarding the IMP, the requirement of added therapy and the outcome.

Moreover, TEAE, TEAE related to IMP and serious TEAE will be presented according to their time to onset in weeks calculated from the start of the period #2 (*resp. #4 and #6*).

AE starting during the run-in period will be also described by SOC and PT in the SS.

All adverse events reported after the last Bumetanide intake + 2 days (excluded) will be listed. All COVID-19 infection reported during the study will be listed.

Number of events as well as number, percentage of patients reporting at least one event, presented by primary System Organ Class (SOC), and Preferred Term (PT), will be provided for all AE and all serious AE occurring after the first intake in the extension part in the patients included in the extension period.

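### The annual adverse event incidence rate divides by whole-period time rather than time at risk, so it understates the rate it names for common events that do not stop treatment

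*SAP*

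**What the plan says.** For events, SAP 3.1.1 lists the number of patients with the event (n), the number of events and the number of patients at risk (N), "as well as the patients-years at risk for the event (NPY), the crude incidence rate and the annual incidence rate calculated as follows". NPY is then defined as the "sum of patient's period duration in years", and the annual rate, also called exposure-adjusted, is 100 × n/NPY. The SAP adds that "the annual incidence rate is interpreted as the number of patients with events per 100 patients-years".

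SAP 3.6.1 applies this to the adverse event tables by system organ class and preferred term: "Number of events as well as number, percentage and annual incidence rate of patients reporting at least one event". Table (3.6) 1 in SAP 3.6 sets the periods. The double-blind treatment-emergent period (#2) ends at "Min(Last intake in double-blind + 2 days, First intake in open-label"), and the other five periods are likewise bounded by intakes, visits or follow-up. The double-blind tables compare two arms. The open-label tables cover only the placebo/bumetanide arm, and the remaining set is also single-arm: "For the combined period: in the SSC on the S95008/S95008 arm".

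The protocol's own adverse event analysis (10.2.2.6.1) specifies counts and percentages only. The annual rate enters with the SAP.

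**The concern.** The label and the formula describe different quantities. Because n counts patients rather than events, a patient who has had the event cannot add to the numerator again, yet keeps adding time to the denominator. That time is not at risk in the sense that n uses. The longer patients stay on treatment after a first event, and the more of them there are, the further the reported rate falls below the rate its name promises.

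The protocol contains an event type of this kind. Section 8.6 states that "AEOSI include any biological Potassium electrolyte abnormality" below 3.5 mEq/L. For mild hypokalaemia, section 8.2 provides dietary advice and "Patient will be supplied with oral potassium according to investigator's opinion", with no instruction there to stop the IMP, so time after the event remains in NPY. Four of the six double-blind Na/K checks in the section 8.2 laboratory table fall by W004. This does not show that onset is early, but it makes early detection plausible, and early onset is where the gap is largest.

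In the double-blind period, if an event is more frequent on bumetanide than on placebo, the larger rate is understated more and the two rates a reader compares are drawn together. In the single-arm periods the only effect is a rate that is too low.

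**Working it through.** The documents state no event rate, so there is no plan figure to reproduce. The check takes the SAP formula as written and compares it with a time-at-risk rate.

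**Inputs.** T = 0.5 year for the 26-week double-blind period and T = 1 year for the 52-week combined period, both from the study plan. The other inputs are assumptions: p, the proportion of patients with the event; t, the time of first onset; f, the fraction of event patients who stop the IMP at onset. Full follow-up is assumed apart from that stopping.

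**Formulas, per 100 patient-years.**

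- SAP rate, no stopping: 100p/T.
- Time-at-risk rate, all first events at t: 100p/[(1−p)T + pt].
- Time-at-risk rate, constant hazard: −100 ln(1−p)/T.
- SAP rate with stopping, period #2: 100p/[(1−p)T + p(1−f)T + pf(t + 2 days)].

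**Direction.** Since t ≤ T, the time-at-risk denominator is never larger than pT + (1−p)T = T. The SAP rate is therefore never above the time-at-risk rate, whatever the onset pattern.

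**Worked case, T = 0.5, t = 2/52 = 0.0385.**

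- p = 0.40: SAP 40/0.5 = 80.0. Time at risk 40/(0.300 + 0.0154) = 126.8.
- p = 0.10: SAP 10/0.5 = 20.0. Time at risk 10/(0.450 + 0.0038) = 22.0.
- Ratio between arms: 4.00 by the SAP formula, 5.76 by time at risk.

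**Range over 26 weeks, no stopping (drug v placebo).**

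| Assumed risks | Onset | SAP rates (ratio) | Time-at-risk rates (ratio) |
|---|---|---|---|
| 40% v 10% | week 2 | 80 v 20 (4.0) | 126.8 v 22.0 (5.76) |
| 40% v 10% | week 13 | 80 v 20 (4.0) | 100.0 v 21.1 (4.75) |
| 40% v 10% | constant hazard | 80 v 20 (4.0) | 102.2 v 21.1 (4.85) |
| 20% v 5% | week 2 | 40 v 10 (4.0) | 49.1 v 10.5 (4.68) |
| 10% v 5% | week 2 | 20 v 10 (2.0) | 22.0 v 10.5 (2.10) |

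A simulation of 500,000 patients at p = 50% with constant hazard gave 99.9 against 138.5. The formulas give 100.0 and 138.6.

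**If event patients stop at onset in both arms (40% v 10%, week 2).** The SAP formula gives 97.9 v 21.0 (4.67) when half stop and 126.0 v 22.0 (5.72) when all stop. For treatment-emergent events the gap nearly vanishes once the event ends treatment. This is the situation below 3 mEq/L of potassium, where Protocol 5.6.1 and 8.2 discontinue the IMP.

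**Single-arm combined period (T = 1, week-2 onset).** p = 0.40: 40 against 40/(0.600 + 0.0154) = 65.0. p = 0.10: 10 against 10/(0.900 + 0.0038) = 11.1.

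**Serious events.** SAP 3.6.1 tabulates serious emergent events and deaths on periods #1, #3 and #5, which run to the end of the study period whether or not the IMP was stopped. A non-fatal serious event that ends treatment can therefore still leave later time in NPY if the patient remains in the study.

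**The case against.** The formula is complete and its reading is stated, so this can be called a labelling fault rather than a wrong calculation. The same sentence uses the at-risk wording for N, the denominator of the crude percentage, so it may simply mean under observation. Nor does the SAP claim to estimate a first-event hazard. With equal follow-up its ratio equals the 26-week risk ratio, and 40% v 10% really is a fourfold risk. When events cluster early, a time-at-risk rate is no ideal summary either, because it too depends on period length. Nothing in the documents supports a 40% event risk, and for events in 2 to 5% of patients the understatement is only about 1 to 5%. The dedicated hypokalaemia summary by severity (SAP 3.6.3) uses numbers and percentages, not NPY.

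Most of this stands, and it limits the consequence. No rate ratio or between-arm adverse event test is planned. Event counts, crude percentages and time to onset are reported alongside, and the hypokalaemia example is affected only where the event is also tabulated as an adverse event. It does not remove the mismatch. If at risk means under observation, then with near-equal follow-up the exposure-adjusted rate is a rescaled percentage and adds almost nothing to the percentage printed next to it.

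**Conclusion.** The concern holds. The denominator is named as time at risk for the event but is whole-period time, and nothing else in the SAP ends a patient's time at first onset. The direction is certain. The size depends on assumed risks and onset times. Over 26 weeks without stopping, the SAP rate falls short by about 2 to 5% for an event in 5% of patients, and by about 16 to 28% at 30%. In each range the first figure assumes constant hazard and the second week-2 onset. The issue matters for common treatment-emergent events that do not lead to prompt stopping, and for non-fatal serious events followed beyond IMP stop. It is worth correcting before the safety tables are produced, but it bears on descriptive safety reporting only and leaves the primary analysis and sample size untouched.

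**What to change.** For each system organ class and preferred term, compute NPY as time from period start to first occurrence for patients with the event, and to the patient's own period end for those without, then report 100 × n/NPY. Alternatively, keep whole-period time, use the total number of events as numerator, call the result an event rate and drop the at-risk wording. Relabelling NPY as total period time is the minimum: it removes the contradiction but leaves a rate that mostly rescales the percentage. Whichever is chosen, direct readers to the planned time-to-onset table, since no single rate describes early-clustering events well.

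The cost is a revision of SAP 3.1.1 and minor programming to give each term its own denominator. Adverse event onset is already needed for the time-to-onset tables in SAP 3.6.1, so no new data are required.

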3.1.2. General definitions

Unless specified otherwise in Sections 3.2 to 3.6, the following definitions will be considered:

Three analysis periods will be defined:

- Double-blind period.
- Open-label period.
- Combined period.

For each, start date, stop date, first and last IMP intake date, baseline and under treatment period will be specified.

- Analysable value will be defined as any non-missing value.
- Baseline value will be defined as the last analysable value prior to the first IMP intake of the considered analysis period (*i.e.* before or the same* date as the first IMP intake date).

Note:

- In case of patient included and/or randomised but not treated (*i.e.* patients with treatment duration equal to 0): value at baseline (for the double-blind or combined period) is defined as the last analysable value prior or equal to date of inclusion visit.
 - * For parameters measured the day of inclusion for the double-blind or combined period (resp. the day of W26 or W26B for open-label period) but before the first IMP intake of the considered period.
- Post-baseline value will be defined as any value recorded at a given timepoint after baseline.
 - Change from baseline will be defined as the arithmetic difference between a post-baseline value and the baseline value of the considered period.

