The **Social Responsiveness Scale, Second Edition (SRS-2)** (Costantino, 2012) is a 65 items, Likert scale, objective measure of symptoms associated with autism. The SRS-2 generates a Total score that serves as an index of severity of social deficits in the autism spectrum.

It will be completed by the parents/legal representative or caregiver (when applicable):

- At Inclusion
- During the Double Blind treatment period at: W004, W012, W026 visits
- During the Open Label treatment period at: W038, W052 visits
- At the withdrawal visit in case of premature withdrawal after visit W000+Day10

It is highly recommended same parent/legal representative or caregiver (when applicable) completes the SRS-2 all along the study.

In the framework of this study the following forms will be completed:

- SRS-2 Preschool form (ages 2 to 4¹/₂)
- SRS-2 School form (ages 4 to 18 yo).

For younger children, some overlap in form age has been provided so that an older pre-schooler can be rated and scored on either Preschool or School age forms. Children in this overlapping period are generally rated on the School-Age Form, excepted for those children with lower functioning, with behaviour more similar to that described on the Preschool Form.

The **Vineland Adaptive Behaviour Scales-Second Edition (VABS II)** is designated to measure adaptive behaviour. It explores 5 domains: Communication, Daily Living Skills, Socialization, Motor Skills and Maladaptive Behaviour.

It will be completed by a Medical Doctor or a Psychologist/ Health professional with:

- o a detailed knowledge and experience of ASD and child development
- o who plays a key role in the current site organization of the team
- o is involved in the diagnosis of ASD patients on a regular basis
- o and has been trained on VABSII with the sponsor training

- At Inclusion
- During the Double Blind treatment period at: W026 visit
- During the Open Label treatment period at: W052 visit
- At the withdrawal visit in case of premature withdrawal after visit W000+Day10

It is highly recommended the same rater with the same parent/legal representative or caregiver (when applicable) completes the VABS II all along the study.

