2. ANALYSIS SETS / TREATMENT GROUPS

2.1. Analysis sets

- The Randomised Set (RS) is constituted of included and randomised (*i.e.* for whom a therapeutic unit was randomly assigned using IWRS) patients.
- The Safety Set (SS) is constituted of all patients having taken at least one dose of IMP.
- Randomised Set Open (RSO) patients of the RS having taken at least one dose of Bumetanide during the open-label period.
- Safety Set Open (SSO): patients of the SS having taken at least one dose of Bumetanide during the open-label period.
- Randomised Set Combined (RSC): patients of the RS having taken at least one dose of Bumetanide during the open-label period and with a delay between end of double-blind period and start of open-label period less than 30 days.
- Safety Set Combined (SSC): patients of the SS having taken at least one dose of Bumetanide during the open-label period and with a delay between end of double-blind period and start of open-label period less than 30 days.

The size of each analysis set, and reasons for exclusion will be described.

Listings of patients with their membership, or not, to each analysis set and of excluded patients with reasons for exclusion will be provided.

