The 100 datasets imputed for the primary analysis and supplementary analysis at W012 (based on the changes from baseline in CARS2 total scores) will be used to derive, the CARS2 responders. Analysis step will be based on the logistic regression model described above and then the combination step will be applied.

Statistical elements: the following elements will be provided in a summary table:

- Estimate (standard error) of the odds ratio between treatment groups.
- Two-sided 95% CI of the estimate.

- Descriptive analysis:

The CARS2 total score and subscores will be summarized using descriptive statistics and graphs (expect for subscores):

- During the double-blind period: baseline, each planned post-baseline visit (W004, W012 and W026) as well as change from baseline to each planned post-baseline visit will be described in the RS by treatment groups (S95008 vs placebo).
- During the open-label period: OL baseline, each OL planned post-baseline visit (W038 and W052) as well as change from OL baseline to each OL planned post-baseline visit will be described in the RSO for the Placebo/S95008 arm.
- During the combined period: baseline, each planned post-baseline visit as well as change from baseline to each planned post-baseline visit will be described in the RSC for the S95008/S95008 arm.
- At the follow-up visit (WEND), the change from the last post-baseline visit under treatment during the open-label period to WEND will be described in the RSO by treatment groups (S95008/S95008 vs Placebo/S95008).

The proportions of CARS2 responders will also be summarized at each planned post-baseline visit for each period.

The proportions of CARS2 performed remotely at baseline, W012 and W026 will be described in the RS by treatment groups (S95008 vs placebo).

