3.4.3.3. Vineland Adaptative Behaviour Scale II (VABS II)

Definition: The main analytical approach will be defined as the change in standard score of each domain from baseline to W026.

Main Analysis: A General Linear Model with the fixed categorical effect of treatment, country and gender as well as the continuous, fixed covariate of baseline will be used for the change in standard score of each domain in the RS.

GENERAL LINEAR MODEL (ANCOVA): $change = baseline\ country\ gender\ treatment$

Missing data handling: for missing data handling, the same approach as for the primary endpoint will be performed. Of note that there is only one post-baseline planned visit (W026) to consider.

Statistical elements: The following elements will be provided in a summary table:

- Estimate (standard error) of the difference between adjusted treatment arm means.
- Two-sided 95% CI of the estimate.

Supplementary analysis:

VABS II standard domains scores, and Adaptative Behavior Composite standard score will be summarized using descriptive statistics and graphs:

- During the double-blind period: baseline, W026 as well as change from baseline to W026 will be described in the RS by treatment groups (S95008 vs placebo).
- During the open-label period: OL baseline, W052 as well as change from OL baseline to W052 will be described in the RSO for the Placebo/S95008 arm.
- During the combined period: baseline, each planned post-baseline visit as well as change from baseline to each planned post-baseline visit will be described in the RSC for the S95008/S95008 arm.

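### The open-label baseline is not tied to W026, so a placebo child with no W026 value has placebo-period change reported as change on bumetanide

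*SAP*

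**What the plan says.** SAP 3.1.2 (General definitions) applies unless SAP 3.2 to 3.6 say otherwise. It states: "Baseline value will be defined as the last analysable value prior to the first IMP intake of the considered analysis period". The only condition on the value is: "Analysable value will be defined as any non-missing value". A note on same-day measurements mentions "resp. the day of W26 or W26B for open-label period) but before the first IMP intake of the considered period". That note settles when a same-day value counts as pre-dose. It shows which visit the authors had in mind, but it does not exclude older values.

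The open-label efficacy set is defined in SAP 2.1: "Randomised Set Open (RSO) patients of the RS having taken at least one dose of Bumetanide during the open-label period". Membership needs one dose and no W026 rating. SAP 2.1 restricts the combined sets (RSC and SSC) to children "with a delay between end of double-blind period and start of open-label period less than 30 days", but places no such condition on the RSO.

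The rule is used in the open-label tables. For CARS2 (SAP 3.4.2.3): "change from OL baseline to each OL planned post-baseline visit will be described in the RSO for the Placebo/S95008 arm". For VABS II (SAP 3.4.3.3): "OL baseline, W052 as well as change from OL baseline to W052 will be described in the RSO for the Placebo/S95008 arm". SRS-2, PedsQL, WHOQOL-Bref and EQ-5D are handled in the same way in SAP 3.4.3.1, 3.4.3.4, 3.4.3.5 and 3.5.1. None of these sections redefines the open-label baseline.

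Protocol 7.2 schedules CARS2 and SRS-2 at inclusion, W004, W012 and W026. After inclusion, VABS II has a single double-blind rating: "During the Double Blind treatment period at: W026 visit".

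**The concern.** For the double-blind period the rule does no harm, because the scales are rated at W000, just before the first dose. For the open-label period it lets an old value stand in for a missing W026 value without any flag.

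The Placebo/S95008 open-label tables are meant to show what happens once placebo children start bumetanide. They have no concurrent control, so the reading depends entirely on where the baseline sits. If it sits inside the placebo period, change that occurred on placebo is reported as change on bumetanide.

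The planned outputs would not reveal this. SAP 3.2.1 lists children with a delay between the periods, but nothing lists children whose open-label baseline comes from a visit before W026. The open-label CARS2 responder proportions (improvement of at least 4.5 points from baseline, SAP 3.4.2.3) would be affected too, if they are computed from the open-label baseline.

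**Working it through.** The plan gives no figure for this point, so there is none to reproduce. The check has two parts.

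**1. Share of the reported change that falls on placebo.** Inputs are the planned visits in Protocol 7.2 and the rule in SAP 3.1.2, for a Placebo/S95008 child with no W026 or W26B value and no unscheduled rating in between.

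Share = (26 − baseline week) / (visit week − baseline week)

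| Scale and baseline used | To W038 | To W052 |
|---|---|---|
| W026 present (intended) | 0/12 = 0% | 0/26 = 0% |
| CARS2 or SRS-2, W012 carried | 14/26 = 54% | 14/40 = 35% |
| CARS2 or SRS-2, W012 also missing, W004 carried | 22/34 = 65% | 22/48 = 46% |
| VABS II, W000 carried | not rated | 26/52 = 50% |

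PedsQL, WHOQOL-Bref and EQ-5D are also planned at W012 and W026 (Protocol 9.2), so the W012 row applies to them at the visits where they are rated.

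Two invented records show the mechanism:
- VABS II is 60 at W000, missing at W026 and 66 at W052. The rule reports 66 − 60 = +6 from open-label baseline, over 52 weeks of which 26 were on placebo.
- CARS2 is 40 at W012, missing at W026 and 36 at W052. The rule reports 36 − 40 = −4, over 40 weeks of which 14 were on placebo.

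**2. Shift in the arm's mean open-label change.**

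Shift = f × d

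Here f is the share of the arm whose baseline is carried from before W026, and d is the mean placebo-period change between that value and W026. The documents give neither, so both are assumed.

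- CARS2, f = 3% to 10%, d = 1 to 2 points: 0.03 × 1 = 0.03 to 0.10 × 2 = 0.20.
- VABS II, f = 3% to 10%, d = 2 to 4 points: 0.03 × 2 = 0.06 to 0.10 × 4 = 0.40.
- CARS2 over a wider range, f = 5% to 20%, d = 0.5 to 3 points: 0.05 × 0.5 = 0.025 to 0.20 × 3 = 0.60.

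For a single affected child the whole of d is misassigned. Against the 4.5-point responder threshold, a d of 1 to 2 CARS2 points is 1/4.5 = 22% to 2/4.5 = 44% of the distance.

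**The case against.** The strongest reply is that the trigger is narrow. Open-label drug is first dispensed at W026 (Protocol 6.2), the visit at which the scales are rated. Protocol 4.2.2 allows that visit to be split over several days and the Vineland and parent questionnaires to be completed up to 3 days earlier. SAP 3.4.2.3 tabulates CARS2 ratings done remotely, so a missed site visit need not mean a missing CARS2 rating. Children who stop treatment in the double-blind period follow a separate visit path (Protocol 4.2.2), so the 15% withdrawal allowance does not feed this problem. All of this stands and limits the number affected, but it does not alter what the rule does when a W026 value is missing.

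It can also be said that the last non-missing pre-dose value is a coherent, prespecified rule, and that these tables carry no p-values (SAP 3.4.1). Both are true. Yet the SAP's own note points to W26 or W26B, and here the rule yields a change that does not match its label.

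A reader might infer three stronger things that the documents do not support:
- **That a delayed open-label start has the same fault because the RSO has no gap limit.** It does not. A W026 value is taken at the end of the placebo period, so no double-blind placebo change is misassigned. Delays are already listed (SAP 3.2.1, and SAP 3.6 for more than 30 days), and W26B may be a repeat visit.
- **That the rule inflates the apparent benefit of bumetanide.** The error follows the placebo-period change in whichever direction that went. CARS2 ratings are made against a typically developing child of the same age (Protocol 7.2), which weakens an appeal to spontaneous improvement.
- **That the SAP predicts many missing W026 ratings because of the pandemic.** SAP 1 says only that a risk assessment was carried out.

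**Conclusion.** The point holds as a minor defect in a stated rule. In the RSO, a Placebo/S95008 child without a W026 or W26B value has a placebo-period value as open-label baseline for CARS2, SRS-2, VABS II, PedsQL, WHOQOL-Bref and EQ-5D. The child's reported open-label change then mixes placebo and bumetanide time.

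The primary analysis and the double-blind secondary analyses are not affected. Nor is open-label CGI-I, which is restricted to comparison with W026 (SAP 3.4.3.2), or the S95008/S95008 arm, which is described from its W000 baseline in the combined period.

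The interval shares follow from the visit schedule alone. The effect on arm means is probably small, within the assumed ranges worked above; no missing rate or placebo-period change in the documents supports or refutes those ranges.

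**What to change.** Add to SAP 3.1.2:

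> For efficacy and quality-of-life scales (CARS2, SRS-2, VABS II, PedsQL, WHOQOL-Bref, EQ-5D), the open-label baseline is the pre-dose value from the W26 visit, or from W26B if performed, including assessments made on the days over which that visit may be split. If there is no such value, the open-label baseline and change from it are missing. The number of such children is reported for each scale.

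The SAP uses W26B without defining it, so the same edit should say what it is. No 30-day limit is needed: it would remove children with a valid W026 rating, and delayed starters are already listed. Laboratory, ECG and vital-sign baselines follow the same general rule and are left as they are here.

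The cost is one sentence and one count per table. A few children leave the open-label change tables but stay in the tables of values by visit. The sample size and all double-blind analyses are unchanged.
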